At the index date, we will define groups in the IBD case population based on mental health phenotype, including a comparator group without mental health comorbidity at the index date, and compare the sociodemographic characteristics of these groups.

Stream 2: Follow-up

We will then describe incidence of each study outcome in the five years after the index date for each group, and the relative incidence of each outcome in those with and without mental health comorbidity.

Stream 2: Study outcomes

These will comprise the following.

Quality of life indicators:

Affective symptoms (depression, low mood, deliberate self-harm, suicidal ideation or parasuicide), IBD symptoms, absence from school, absence from work, unemployment, substance abuse, and sleep problems. IBD symptoms will comprise; abdominal pain, discomforts or bloating, diarrhoea, weight loss, growth retardation and tiredness/fatigue. (See Appendix 1 – Table s1 for Read Codes and SNOMED codes).

IBD severity indicators:

Medication use, surgical intervention, nutritional supplement use, and markers of nutritional status. Surgical intervention will comprise any abdominal surgery, and stoma formation (as a separate outcome). Medication use will comprise use of: rectal 5-aminosalicylic acid (5-ASA), oral 5-ASA, rectal steroids, oral steroids, antimetabolites, tumour necrosis factor inhibitors (TNFi) and other biologic therapies. The latter of these groups may not be well captured in primary care and if so this will be reported in the limitations section of the final study manuscript. Nutritional supplements will comprise the five most prescribed nutritional supplements: Modulen, Fortisip, Ensure, Osmolite, and Neocate. Nutritional markers will comprise; being underweight (under the 5th centile of weight for height or BMI < 18.5 kg/m² after age 18) and growth retardation related codes. (See Appendix 1 – Table s2 for Read Codes and SNOMED codes).

Healthcare resource utilisation:

Primary care attendances and hospital admissions. Hospital admissions will be separated into general admissions (including those for IBD) and psychiatric admissions. (See Appendix 1 – Table s2 for Read Codes and SNOMED codes).

Stream 2: Statistical methods

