We will use standard descriptive statistics (mean, standard deviations, etc) to describe the characteristics of the study cohort overall and by mental health phenotype. Across mental health condition phenotypes we will describe the incidence of recording of all the quality-of-life indicators, IBD severity markers, and healthcare resource utilisation outcomes up to five years after the index date (01/01/2015), compared to incidence in the group without mental health conditions. The end of follow-up will be the first of; 01/01/2020 (5 years after the index date) we will not follow patients up into 2020/21 due to changes in patient health behaviour and primary care interactions due to COVID-19, the patient's 25th birthday, date of loss to follow-up (either deregistration or death). All individuals contributing at least six months of follow-up time in the analysis will be included. We will not follow patients up into 2020/21 due to changes in patient health behaviour and primary care interactions due to COVID-19.

Relative incidence between those with and without mental health conditions will be estimated for repeated events (e.g. number of hospital admissions) and binary events (e.g. quality of life indicators) using, as appropriate, Poisson regression, negative binomial regression (if we need to account for overdispersion), or zero-inflated Poisson regression (if we need to model rare events). To account for variable duration of follow-up, we will include the natural logarithm of person-years of follow-up as a model offset. Confidence intervals will be estimated using robust SEs. Models will be adjusted for age, gender, socioeconomic status, ethnicity, and other childhood conditions (asthma, atopic dermatitis, allergic rhinitis, thyroid disease, epilepsy, diabetes, cancer, juvenile idiopathic arthritis (JIA) including systemic JIA, systemic lupus erythematosus (lupus), ankylosing spondylitis (AS) and psoriatic arthritis). Statistical significance for analyses will be reported using P values and 95% confidence intervals as appropriate.

Where numbers allow, we will report absolute and relative incidence in subgroups by, mental health condition group, age group (5-<12; 12-<16; 16-<18; 18-<25) (child, adolescent, young adult), and sex.

References

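### Stream 2 allows zero-inflated Poisson because events are rare, but rarity is not excess zeros; for rare repeated counts the count-part ratio can miss the planned relative incidence

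*Combined protocol and SAP*

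**What the plan says.** The target is the same in two places. *Stream 2: Follow-up* promises "the relative incidence of each outcome in those with and without mental health comorbidity". *Stream 2: Statistical methods* says: "Relative incidence between those with and without mental health conditions will be estimated for repeated events (e.g. number of hospital admissions) and binary events". The second section names quality-of-life indicators as its example of binary events and number of hospital admissions as its example of repeated events.

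The models are listed in that section. Poisson comes first, under an as-appropriate qualifier, for both kinds of event: "binary events (e.g. quality of life indicators) using, as appropriate, Poisson regression". The alternatives are "negative binomial regression (if we need to account for overdispersion), or zero-inflated Poisson regression (if we need to model rare events". Two further specifications apply: "we will include the natural logarithm of person-years of follow-up as a model offset" and "Confidence intervals will be estimated using robust SEs".

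The plan gives no criterion for excess zeros. It does not say what enters the zero part of a ZIP model, whether the offset belongs to one part or both, which coefficient will be reported, or how the two parts would be turned into one incidence ratio.

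**The concern.** A ZIP model treats patients as a mixture. One group can never have the event; in the other, counts follow a Poisson. Its count coefficient is a rate ratio among patients who are able to have the event. Any effect of mental illness on whether a patient is in that group at all goes into the zero part. If ZIP is chosen because an outcome is rare, and its count coefficient is then reported as relative incidence, the rare count outcomes carry a different quantity from the common ones under the same label.

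The outcome most exposed is psychiatric admissions, which *Stream 2: Study outcomes* separates from general admissions. They are part of healthcare resource utilisation, a Stream 2 secondary objective. An effect of mental illness on who is ever admitted is plausible there, and it is the kind of effect that a count coefficient leaves out.

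**Working it through.** The plan gives no sample size, event rate or effect size for Stream 2, so there is no figure of its own to reproduce. The check has four steps.

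**1. Does rarity imply excess zeros?** Under a Poisson with mean m, P(0) = exp(−m).
- m = 0.05: exp(−0.05) = 95.1% zeros.
- m = 0.02: exp(−0.02) = 98.0% zeros.

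Neither has any zero inflation, so a high share of zeros does not identify the ZIP model.

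**2. When does the count ratio equal relative incidence?** In a ZIP with always-zero share π and count mean μ, the overall mean is (1 − π) × μ. With subscript 1 for mental health comorbidity and 0 for none:

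relative incidence = [(1 − π₁)/(1 − π₀)] × count ratio.

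The two agree only if π₁ = π₀.

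| π₀ | π₁ | Count ratio | Relative incidence |
|---|---|---|---|
| 95% | 95% | 2.0 | (0.05/0.05) × 2.0 = 2.0 |
| 95% | 90% | 1.0 | (0.10/0.05) × 1.0 = 2.0 |
| 95% | 97.5% | 2.0 | (0.025/0.05) × 2.0 = 1.0 |

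The second row hides a real doubling and the third shows a false one, so the error can go either way.

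**3. Size for repeated counts.** From the plan: follow-up between six months and five years, and a log person-years offset. Assumed: 1,500 patients, 25% with a mental health condition, follow-up uniform over that range, about 94% zeros.

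*(a) Exposure changes who is affected.* The share able to have the event is 10% without and 15% with a mental health condition, at 0.3 events per year in both. The true relative incidence is 0.15/0.10 = 1.5 and the true count ratio is 1.0. In 150 runs:

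| Model | Ratio |
|---|---|
| Poisson | 1.48 |
| ZIP, constant zero part | 1.26 |
| ZIP, exposure in the zero part | 0.97 |

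A separate 200-run set on the same inputs gave 1.51, 1.26 and 0.96. A third set assumed 2,000 patients, 20% exposed, shares of 5% and 10% and a true ratio of 2.0. Its medians were 1.97, 1.19 and 1.01, and the share of runs significant fell from 78% with Poisson to 10% and 7%. Those significance shares are indicative only, because the ZIP standard errors were approximate and not robust.

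Combining both parts of the ZIP with exposure in the zero part gave 1.50 (SD of log ratio 0.24). Combining cannot help the constant version: there π₁ = π₀ by construction, so its overall ratio is the same 1.26.

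*(b) Plain rare Poisson counts*, 0.02 per year and true ratio 1.5. ZIP with a constant zero part matched Poisson (both 1.50, SD 0.22, in a 200-run set). ZIP with exposure in the zero part raised the SD of the log ratio from 0.23 to 0.44 (0.22 to 0.42 in the other set). Nothing was gained, since there was no inflation to model.

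**4. Strictly 0/1 outcomes.** A 0/1 variable with mean p has variance p(1 − p), below the Poisson value p, so it shows no overdispersion relative to Poisson. All three models gave the same ratio: 1.50 where the truth was 1.5 (1.49 in another set), and 1.95 where it was 2.0. The fitted inflation was about zero, so ZIP collapsed to Poisson.

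**The case against.** The case against has real force, and several stronger readings should be resisted.

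*A reader might infer that all Stream 2 results are at risk, including parasuicide and stoma.* They are not. The primary objective concerns quality-of-life indicators, which the plan treats as binary, and parasuicide is one of them. Stoma formation reads naturally as ever/never. Step 4 shows no harm for such outcomes. They would be exposed only if analysed as repeated counts.

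*A reader might infer that the plan switches to ZIP whenever events are rare.* The wording is softer: as appropriate, and if needed, with Poisson first. What stands is that no other criterion for ZIP is written.

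*A reader might infer that rarity alone produces bias.* It does not. With plain Poisson counts the ZIP ratio is not biased, and only the version with exposure in the zero part loses precision. The 1.26 and 0.97 arise in data simulated with structural zeros that differ between the groups.

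*A reader might infer that 0.97 is a faulty estimate.* It estimates the count-part ratio, truly 1.0 in that scenario. It becomes wrong when labelled relative incidence. The plan does not say that it would be so labelled, and a careful analyst could combine the parts. But nothing requires that, and with a constant zero part combining changes nothing.

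The plan also describes incidence in each group, so a raised incidence beside a null ratio might be noticed. That helps detection, but it does not define the adjusted estimate.

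**Conclusion.** The point holds for rare repeated counts. The stated reason for ZIP is the wrong one, and its count-part ratio is in general not the planned relative incidence. That second statement is algebra and rests on no simulated input. Its size does: with a true ratio of 1.5, the reported ratio could fall to 1.26 or 0.97, or precision could drop with the SD of the log ratio at 0.44 instead of 0.23. These figures depend on the assumed sample size, exposure share, event rates and mechanism. The 0.97 also depends on the count coefficient being reported alone, and the 1.26 on a constant zero part. For strictly 0/1 outcomes ZIP does no harm and adds nothing.

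This should be fixed. It is not critical: the clear case is psychiatric admissions, one component of a secondary objective.

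**What to change.** Amend *Stream 2: Statistical methods* before the outcome data are analysed:

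1. Remove rarity as the reason for ZIP.
2. Use log-link Poisson with the planned person-time offset and robust standard errors for all binary outcomes and all rare outcomes.
3. Allow negative binomial only for overdispersed repeated counts.
4. If ZIP is kept at all, limit it to demonstrated excess zeros by a criterion stated in advance. Specify the zero part, including whether exposure and the offset enter it; a constant zero part forces the always-zero share to be equal in the two groups. Report the overall (marginal) incidence ratio from both parts combined, with its confidence interval.

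The cost is a few lines of wording and no new data. At most, the count distribution is fitted slightly less well where zeros are truly in excess. Penalised estimation, a smaller covariate set or a minimum event count for sparse outcomes are separate choices that this point does not require.

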To evaluate the magnitude of potential bias from including, as matched controls, people who are registered with GP practices but who do not attend their practice, we also repeated the primary analysis including only controls with a least one primary care consultation in the year preceding their index date.

All statistical analyses were performed using R statistical package software version 3.4.1. The study was conducted in line with the RECORD (Reporting of studies conducted using observational routinely collected data) guidelines.(13)

Stream 2:

Stream 2: Study design

The proposed study will use the retrospectively collected data of all eligible patients within the database at the date of data extraction. Within this primary care cohort, all patients with IBD will be identified using diagnostic codes and prescription records. A diagnostic algorithm will be developed to facilitate robust case identification of IBD and IBD subtypes as well as mental health outcomes.

Stream 2: Study cohort

The eligible IBD cases will comprise all prevalent cases of IBD aged under 25 at 01/01/2015 (index date) comprising of the three main subtypes; ulcerative colitis (UC), Crohn's disease (CD) and IBD unclassified (IBDU), excluding microscopic colitis, radiation induced enterocolitis and drug-induced enterocolitis. We will extract sociodemographic details for all individuals. Sociodemographic data will comprise by age group, age at diagnosis, sex, ethnicity, and socioeconomic status. Ethnicity will be categorised as follows to be consistent with the UK official census categories: White, Asian, Black African/Caribbean, Mixed, and Other. The index of multiple deprivation (IMD) will be used as a measure of socioeconomic status. This is derived from patient postcode at the point of data extraction.

We will identify comorbid psychological condition groups in all people with PIBD. These will comprise 3 composite phenotypes; anxiety/panic disorders, major depression or depressive episodes, and other psychological conditions. Other psychological conditions will be a composite of; eating disorders, body image disorder, attention-deficit disorder (ADHD), behavioural disorders, adjustment disorder, acute stress disorder, schizophrenia, bipolar disorder and post-traumatic stress disorder (PTSD). Where numbers are sufficient, subgroups of the broad 'other psychological conditions' composite may be examined.

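### Stream 2 uses one person-years denominator to the 25th birthday for every outcome, which dilutes the unadjusted group rates of absence from school and other age-limited outcomes

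*Combined protocol and SAP*

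**What the plan says.** The Stream 2 cohort is "all prevalent cases of IBD aged under 25 at 01/01/2015 (index date"), with no lower age limit (Stream 2: Study cohort). Under Stream 2: Statistical methods, follow-up ends at the first of 01/01/2020, "the patient's 25th birthday, date of loss to follow-up (either deregistration or death"). On minimum follow-up the section says: "All individuals contributing at least six months of follow-up time in the analysis will be included". To handle unequal follow-up in the rate models, "we will include the natural logarithm of person-years of follow-up as a model offset".

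The quality-of-life indicators, which carry the Stream 2 primary objective, include "IBD symptoms, absence from school, absence from work, unemployment, substance abuse, and sleep problems" (Stream 2: Study outcomes). The IBD-symptoms indicator is made up of "abdominal pain, discomforts or bloating, diarrhoea, weight loss, growth retardation and tiredness/fatigue". Growth-retardation codes appear again under IBD severity as a nutritional marker. None of these has an at-risk age range. The only age rule in that section concerns the underweight marker, whose definition changes at 18.

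Two kinds of result are planned. The first is descriptive: "We will then describe incidence of each study outcome in the five years after the index date for each group" (Stream 2: Follow-up), set against the group without mental health conditions. The second is a modelled relative incidence, adjusted for age and other covariates. Absolute and relative incidence by age group (5-<12, 12-<16, 16-<18, 18-<25) are also planned, if numbers allow.

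**The concern.** A rate is interpretable only if its denominator is time during which the event could be counted. A patient aged 19 at index can contribute five person-years to the school-absence denominator and almost no chance of an event. A patient aged 17 contributes five, of which about one is at school age.

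There are two consequences. The absolute rate in each group is too low by a factor that depends only on the age mix. And if the groups differ in age, they are diluted by different amounts, so the crude comparison between them partly measures age. The age adjustment in the plan belongs to the regression models, and none is stated for the descriptive group rates. A reader of those rates could see little or no excess of school absence in patients with mental illness where one exists.

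**Working it through.** The documents state no rate, event count or age distribution for this outcome, so there is no planned figure to reproduce.

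**Inputs from the protocol:** start 01/01/2015, end 01/01/2020 or the 25th birthday, at least six months of follow-up (so index age up to 24.5).

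**Assumptions:** index ages from 5, school age from 5 to 18 (ends of 16 and 19 also tried), no early loss to follow-up, and four shapes for the age distribution.

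**Step 1: dilution of the absolute rate.** For index age *a*:

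- person-years = min(5, 25 − *a*)
- school-age person-years = min(5, 18 − *a*), floored at 0
- dilution factor = total person-years / school-age person-years

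Uniform ages:
- Total: 15 × 5 (ages 5 to 20) + 12.375 (ages 20 to 24.5) = 87.375.
- School-age: 8 × 5 (ages 5 to 13) + 12.5 (ages 13 to 18) = 52.5.
- Share 52.5 / 87.375 = 60%; factor 1.66.

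Linearly rising ages (weight *a* − 5):
- Total: 562.5 + 205.875 = 768.4. School-age: 160 + 120.83 = 280.8.
- Share 280.8 / 768.4 = 36.5%; factor 2.74.

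| Index ages | Share at school age (end at 18) | Factor, end at 18 | Factor, end at 16 | Factor, end at 19 |
|---|---|---|---|---|
| Linearly falling | 79% | 1.26 | 1.45 | 1.19 |
| Uniform | 60% | 1.66 | 2.06 | 1.52 |
| Linearly rising | 37% | 2.74 | 4.13 | 2.29 |
| Quadratically rising | 23% | 4.45 | 8.15 | 3.42 |

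**Step 2: crude comparison of groups.** Expected crude ratio = true ratio × (school-age share in the mental health group / school-age share in the comparator). Take a true ratio of 1.5 and let the prevalence of mental illness rise linearly from age 5 to 25.

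- Prevalence 5% to 30%, uniform ages: shares 6.135 / 13.973 = 0.439 and 46.365 / 73.402 = 0.632; ratio 1.5 × 0.439 / 0.632 = 1.04. Rising ages: 1.5 × 0.260 / 0.391 = 1.00.
- Prevalence 2% to 40%, uniform ages: 1.5 × 0.391 / 0.649 = 0.90. Rising ages: 1.5 × 0.236 / 0.407 = 0.87.

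Simulation of the same scenarios gave 0.99 to 1.06 and 0.87 to 0.90. Giving the two groups different age shapes outright is more extreme. A rising-age mental health group against a uniform comparator gives 1.5 × 0.365 / 0.601 = 0.91, and a quadratically rising one gives 1.5 × 0.225 / 0.601 = 0.56. With a true ratio of 2.0 these become 1.22 and 0.75. With equal age distributions the ratio stays at its true value.

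**Step 3: the age-adjusted model.** Poisson models with the protocol's offset were fitted to 200,000 simulated patients, with a true ratio of 1.5. The two columns are a quadratically and a linearly rising mental health group, each against a uniform comparator.

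| Age term | Quadratic rise | Linear rise |
|---|---|---|
| None | 0.55 | 0.92 |
| Linear | 1.34 | 1.61 |
| Quadratic | 1.47 | 1.51 |
| Protocol age bands, age at index | 1.39 | 1.49 |
| No age term, school-age offset | 1.45 | 1.52 |

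The last row shows the simulation error around 1.5. Against it, the clearest residual bias is with a linear age term.

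**Step 4: the planned age bands.** The protocol does not say whether the bands use age at index or attained age. With age at index, uniform within band and school age to 18, the at-risk share is 100% for 5-<12, 15.5 / 20 = 78% for 12-<16, and 1 / 5 = 20% for 16-<18. With attained age, the three younger bands contain only school-age time.

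**The case against.** The strongest reply is that the Stream 2 primary objective is an association, estimated by models that the protocol adjusts for age, and that those models hold up. This largely stands. No age-adjusted scenario reversed the direction, and a flexible age term came close to the truth. The plan does not, however, state how age enters.

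A second reply is that the age-band rates separate adults from children. That is so only if numbers allow and the bands use attained age. With age at index, the 16-<18 band is still about 80% adult time. The planned comparison of sociodemographic characteristics would reveal an age imbalance but would not correct the rates.

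A third is that the protocol counts recordings, and the school code list in Appendix 3 (sTable 3.1) has no age limit. Some entries, such as school phobia or having left school, could be made after 18. This stands: a reader might infer that these outcomes cannot newly occur in adults, and the documents do not say that. For growth retardation the code list is still empty, so what it would capture cannot be checked, and no figure is offered for it here. As a component of the IBD-symptoms indicator it sits beside symptoms that adults do have, so an age cut on that composite would be wrong.

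Finally, the size depends on ages and prevalence gradients that the documents do not give. That the mental health groups are older is plausible but not stated, and one of the three phenotypes includes attention-deficit and behavioural disorders.

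**Conclusion.** The gap is real and confined mainly to the descriptive results. As written, the unadjusted school-absence rates for each mental health group include adult person-years. With school age ending at 18, they are diluted about 1.7-fold for uniform index ages and 2.7-fold for linearly rising ages (1.3- to 4.5-fold over the shapes tried, 1.19- to 8.15-fold over ends from 16 to 19). If the mental health groups are older, the crude comparison is pulled towards or below 1: 0.87 to 1.06 for a true 1.5 under the prevalence gradients tried, and lower under the most extreme age contrast.

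Two stronger readings are not supported. One is that the rates are certainly far too low: without an age distribution the factor could be as small as 1.2 to 1.3. The other is that the Stream 2 association itself will reverse: the age-adjusted ratios are mostly protected, with some residual bias if age enters only linearly, and even the crude ratio is undistorted when the groups have the same ages.

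The same gap exists in mirror image for absence from work and unemployment, where young children add person-years.

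**What to change.** Before analysis, add at-risk ages for the age-limited outcomes.

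- **Absence from school:** count events and person-time only within a pre-specified school-age window, for example from age 5 to the 18th birthday, with sensitivity analyses ending at 16 and 19. Exclude patients with no time in the window. Use this person-time as both the rate denominator and the offset.
- **Absence from work and unemployment:** apply the mirror rule, a pre-specified minimum working age.
- **Growth-retardation codes:** apply an upper age only where they are the stand-alone nutritional marker, and leave the IBD-symptoms composite on full follow-up.
- **Models and age bands:** state how age enters the models (preferably not only as a linear term) and that the age bands use attained age.

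The cost is an outcome-specific start and end date in the person-time code. The downside is that a few codes recorded outside a window will not be counted, and the cut-offs have to be chosen and justified in advance.
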